
Other Secondary^b To compare mirikizumab to placebo with respect to clinical response and time to clinical response during the induction dosing period, and with respect to patient-reported outcomes during the induction dosing period
 
To assess whether 250 mg mirikizumab Q8W and 125 mg mirikizumab Q8W dosing is superior to placebo with respect to maintenance of high and highest levels of clinical response among patients who have an PASI 90 at Week 16 and are re-randomized
 
To assess the efficacy of 250 mg mirikizumab Q8W following relapse after re-randomization to placebo treatment in the Maintenance Dosing Period
 
To evaluate the pharmacokinetics and pharmacokinetic/pharmacodynamic relationship of mirikizumab
	
At Week 16 and various time points over the first 16 weeks of dosing:
 
 • Proportion of patients achieving PASI 90. • Change in PPASI total score in patients with palmoplantar involvement at baseline • Change in PSSI total score in patients with scalp involvement at baseline • Change in NAPSI total score in patients with fingernail involvement at baseline • Change from baseline on the SF-36 physical component summary (PCS) and mental component summary (MCS) • Change from baseline on PatGA of disease severity • Change from baseline for the WPAI-PSO scores (Absenteeism, Presenteeism, Work Productivity Loss, and Activity Impairment) • Change from baseline in QIDS-SR16 total score in those with a baseline QIDS-SR16 total score ≥ 11 
At Week 52 and at various time points during the Maintenance Dosing Period:
 
 • Time to relapse (the loss, at any visit, of $\geq 50\%$ of the Week 16 PASI improvement from baseline) • Proportion of patients who have relapsed • Proportion of patients maintaining clinical response (PASI 90) after re-randomization at the start of the randomized withdrawal period • Incidence of disease rebound within 12 weeks (worsening of psoriasis severity over baseline sPGA score, or worsening of psoriasis severity over baseline PASI score by 125%, or change in psoriasis phenotype [for example, from plaque to pustular]) after re-randomization to placebo at Week 16 
During the Maintenance Dosing Period:
 
 • Proportion of patients who regained PASI 90 within 16 weeks after mirikizumab retreatment • Clearance and volume of distribution of mirikizumab • Relationship between mirikizumab exposure and efficacy (sPGA and PASI)

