Study I6T-MC-AMAK (AMAK) is a Phase 3, multicenter, randomized, double-blind, placebo-controlled, parallel-group, multi-period study in which approximately 500 patients will be randomized to treatment groups involving different mirikizumab doses and regimens or placebo. The study is comprised of 2 treatment periods (Induction and Maintenance with Randomized Withdrawal), which together last for up to 52 weeks, followed by a 12-week Post-Treatment Follow-Up period. [Figure AMAK.5.1](#) illustrates the study design.

Screening Period: Patients will be evaluated for study eligibility ≤ 28 days before the baseline visit (Visit 2). Electronic diary collection will begin at screening.

Baseline and Double-Blind Induction Period (Week 0 to Week 16): At Visit 2 (Week 0; baseline), patients who meet the study eligibility criteria will be randomized 4:1 to receive 250 mg mirikizumab or matching placebo subcutaneously (SC), respectively, at Weeks 0, 4, 8, and 12. Patients who discontinue the study for any reason during this period will stop treatment and continue to the early termination visit (ETV) and then complete the 12-week Post-Treatment Follow-up Period.

[figure not shown]
Double-Blind Maintenance Period (Week 16 to Week 52): All patients who complete the Induction Period may continue in the Maintenance Period. The Maintenance Dosing Period will be a double-blind treatment period with randomized withdrawal. The first injection of study drug for this period will be at Week 16, with the last injection at Week 48. At Week 16 (Visit 7), patients who enter the Maintenance Period will be classified as a responder (Psoriasis Area and Severity Index [PASI] ≥ 90) or non-responder (PASI < 90). All patients will receive injections once every 4 weeks (Q4W) at Weeks 16 through 48 in order to maintain study blind across the study treatment groups. Patients will be treated as follows:

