- Patients who were responders to mirikizumab in the blinded Induction Period (responder definition is PASI 90 at Week 16) will be re-randomized 1:1:1 to 250 mg mirikizumab once every 8 weeks (Q8W), 125 mg mirikizumab Q8W, or placebo Q8W, according to their randomized treatment assignment at Week 16. Patients who relapse during the blinded Maintenance Period (see relapse criterion defined in [Table AMAK.6.5](#)) will remain on, or will be switched to, 250 mg mirikizumab for the remainder of the study and will be monitored for recapture of efficacy response. These patients will begin retreatment with mirikizumab at the visit at which relapse is identified and will receive another mirikizumab treatment at the next visit 4 weeks later. Subsequent mirikizumab treatments will be given at Q8W intervals.
- Patients who received placebo in the blinded Induction Period who are responders at Week 16 (Visit 7) will continue to receive placebo during the Maintenance Period until relapse.
- Patients who were not responders to mirikizumab in the blinded Induction Period will receive 250 mg mirikizumab Q8W. Continued blinded treatment for nonresponders is provided so that partial or slow responders may remain in the study beyond Week 16, thus, maintaining the study blind while patients continue to receive potentially beneficial longer-term treatment with mirikizumab.

- Patients who received placebo in the blinded Induction Period who are nonresponders at Week 16 (Visit 7) will receive 250 mg mirikizumab Q4W for Weeks 16 through 32 and mirikizumab treatments Q8W, thereafter.

At Week 52, patients may enter the long-term extension study, I6T-MC-AMAH (AMAH), or discontinue study treatment and complete Study AMAK's 12-week Post-Treatment Follow-Up Period. Patients who discontinue the study will stop treatment and continue to the ETV and then complete the 12-week Post-Treatment Follow-Up Period.

Post-Treatment Follow-Up Period (12 Weeks): Patients who do not enroll into Study AMAH or who discontinue early from study treatment in Study AMAK will complete the Post-Treatment Follow-Up Period (Visit [V] 801 and V802) of Study AMAK.

Abbreviations: LV = last study visit; miri = mirikizumab; Q4W = every 4 weeks; Q8W = every 8 weeks; V = visit; W = week; w = weeks.

Note: Randomizations occur at Week 0 and Week 16.

* Option to enter Study AMAH or to enter the Post-Treatment Follow-Up Period.

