6.1.2. Study Time Intervals

Table AMAK.6.3 displays a list of study periods along with the definition of which patients will be considered to have entered the study period and when the individuals start and end the study period. The table shows both a date and a time.

To calculate the length of any time interval or time period in this study, the following formula will be used:

$$\text{Length of interval (days)} = \text{End Date} - \text{Interval Start Date} + 1$$

To convert any time length from days to years, the following formula will be used:

$$\text{Length of interval (years)} = \text{Length of interval (days)} / 365.25$$

To convert any time length from days to weeks, the following formula will be used:

$$\text{Length of interval (weeks)} = \text{Length of interval (days)} / 7$$

Only for the purpose of calculating the length of study period time intervals, the words “prior to” in [Table AMAK.6.3](#) should be understood to mean “the day before,” while the word “after” should be understood to mean “the day after.”

Table AMAK.6.3. Definition of Study Period Time Intervals

Study Period	Start Definition	End Definition
Screening: All patients who sign informed consent are considered as entering the Screening Period.	Informed consent date	Prior to the start of induction.
Induction Period Interval: All patients who are randomized to the study are considered as entering the Induction Period.	At the first injection date/time ^a following randomization. For patients who are randomized but not dosed, the Induction Period starts on the date of randomization.	Prior to the start of maintenance. For patients who discontinue before or on the Week 16 visit, the induction period ends at the last date of treatment discontinued date or last treatment visit date.
Maintenance Period Interval: All patients who had any Week 16 to Week 52 visits (except the ones who discontinued the study at Week 16) are considered to have entered the Maintenance Period.	At the Week 16 dosing date/time ^a . If a patient is unable to be dosed at the Week 16 visit, the Maintenance Period starts at the Week 16 visit. If the patient misses the Week 16 visit, the Maintenance Period starts at Day 118.	After the Week 52 visit date. If patients discontinued prior to Week 52, the Maintenance Period ends at the last date of treatment disposition date or last treatment visit date. If the patient relapsed, the Maintenance Period ends before the patient entered the relapse period.

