Relapse Period Interval: All patients who responded during induction and meet the relapse criteria and receive a 250 mg dose during maintenance will be considered to have entered the Relapse Period.	The date/time ^a the patient received the first dose ^a after the patient was measured to meet the relapse criteria.	After the Week 52 visit date. If patients discontinued prior to Week 52, the Relapse Period ends after the early treatment discontinuation visit date.
Placebo Withdrawal Interval: All patients who are re-randomized to placebo will be considered to have entered the placebo withdrawal period.	Same as start of the maintenance period.	Same as end of the maintenance period.
Follow-up Period Interval: All patients who had Visit 801 or 802 are considered to have entered the Follow-up Period.	The latest of the following dates: (1) after the end of the Induction Period; (2) after the end of the Maintenance Period; (3) after the end of end of the Relapse Period.	The last date of the last study visit and study disposition date.

Study Period	Start Definition	End Definition
All Miri^b: All patients who are treated with mirikizumab are considered to have entered this period.	The date/time ^a of first injection with mirikizumab (i.e., injection with placebo does not start the period).	If the patient is not re-randomized to Placebo, then the All Miri Period ends the latest of the following dates: (1) after the end of the Induction Period; (2) after the end of the Maintenance Period; (3) after the end of end of the Relapse Period. If the patient is re-randomized to Placebo, then the All Miri Period is the combination ^b of the Induction and Relapse Periods (if the patient relapses).
All Miri + Placebo Withdrawal Period: All patients who are treated with mirikizumab are considered to have entered this period.	The date/time ^a of first injection with mirikizumab (i.e., injection with placebo does not start the period).	The latest of the following dates: (1) after the end of the Induction Period; (2) after the end of the Maintenance Period; (3) after the end of end of the Relapse Period.
All Miri + Placebo Withdrawal + FUP Period: All patients who are treated with mirikizumab are considered to have entered this period.	Same as the “All Miri + Placebo Withdrawal Period.”	After the last study visit.

Abbreviations: FUP = follow-up; Miri = mirikizumab.

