6.3.2. Mixed-effects Model for Repeated Measures (MMRM)

The MMRM method can be justified based on the hypothetical strategy (ICH E9R1) for handling intercurrent events. In this strategy, the scientific question of interest is to assess the effect of study treatment in a hypothetical trial where all patients have complete data and continue to take study treatment without dropping out of the study or receiving rescue therapy.

MMRM will be used where specified for longitudinal continuous measurements. It assumes missing data can bias results, but the bias can be attenuated by modeling random effects using the within-patient error correlation structure. These correlations between the repeated measurements provide the platform used to account for the bias from patient dropout. MMRM model details are provided in [Section 6.1.4](#).

If patients enter the Relapse Period, only the visits prior to entering the Relapse Period will be included in the MMRM model for the Maintenance Period efficacy analysis.

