		Time to first regaining PASI 90 or PASI 100 (i.e., 2 different analyses) after relapse	For patients who are observed to regain response during the Relapse Period, time will be from the start of the Relapse Period to the first measurement date where response was achieved.	Patients who are not observed to regain response will be censored after the date of their last visit during the Maintenance Period.
		Cumulative time with PASI 90 response after re-randomization through Week 52	Area under the curve (AUC) of PASI 90 response over time using trapezoidal rule (i.e. 100% when patients are PASI 90 responders at the visit and 0% when patients are non PASI 90 responders at the visit.) percentages of scheduled visits with PASI 90 response among all scheduled visits percentages of weeks with PASI 90 response	NRI if the observed value is missing.
		Relapse	The loss, at any visit, of $\geq 50\%$ of the Week 16 PASI improvement from baseline. That is, a patient will have relapsed during the Maintenance Period if their PASI score increases to greater than or equal to the midpoint between their baseline and Week 16 PASI score.	Missing if baseline, Week 16 or observed value is missing.
sPGA	Static Physician Global Assessment (sPGA): the physician's global assessment of the patient's psoriasis lesions at a given time point. Plaques are assessed for induration, erythema, and scaling, and an overall rating of psoriasis severity is given using the anchors of: clear (0), minimal (1), mild (2), moderate (3), severe (4), or very severe (5).	sPGA score	Range from 0 to 5: clear (0), minimal (1), mild (2), moderate (3), severe (4), or very severe (5).	Single item, missing if missing.
		sPGA (0,1) (Primary)	An sPGA assessed as either 0 or 1, which represents a clinically meaningful response of minimal plaque severity or complete resolution of plaque psoriasis.	Missing if sPGA is missing.
		sPGA (0)	An sPGA assessed as 0, which represents a clinically important endpoint indicating complete resolution of plaque psoriasis.	Missing if sPGA is missing.

Measure	Description	Variable	Derivation/Comment	Definition of Missing Components

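### SAP Table AMAK.6.5 times regain of response from the Relapse Period but censors non-regainers in the Maintenance Period; under Table AMAK.6.3 that is about day 0, leaving only regainers in the Kaplan-Meier curve

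*SAP*

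**What the plan says.** The row for time to first regaining PASI 90 or PASI 100 after relapse is in SAP Section 6.10, Table AMAK.6.5. For patients who regain response, "time will be from the start of the Relapse Period to the first measurement date where response was achieved". For the others, "Patients who are not observed to regain response will be censored after the date of their last visit during the Maintenance Period". Table AMAK.6.6 schedules a Kaplan-Meier analysis of time to regaining PASI 90 in the Re-randomized Relapsed population and refers back to Table AMAK.6.5 for the censoring rule.

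The periods are defined in SAP Section 6.1.2, Table AMAK.6.3:

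- End of Maintenance for a relapser: "If the patient relapsed, the Maintenance Period ends before the patient entered the relapse period".
- Start of Relapse: the first dose after the relapse criteria are measured as met.
- End of Relapse: after Week 52, or earlier for dropouts: "If patients discontinued prior to Week 52, the Relapse Period ends after the early treatment discontinuation visit date".

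SAP Section 5 ties that first dose to the relapse visit: "These patients will begin retreatment with mirikizumab at the visit at which relapse is identified".

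**The concern.** The clock runs in one period and the censoring date is taken from another that has already closed. If a non-regainer's last Maintenance Period visit is the relapse visit, that patient contributes about zero follow-up and is never at risk when a regain is recorded. The censoring is then fully informative, because it depends on never regaining. The resulting curve is the distribution of regain times among patients who did regain, presented as the probability of regaining.

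Efficacy of retreatment after relapse is a protocol objective, and this is the analysis in Table AMAK.6.6 that describes how long recapture takes. A curve that climbs to 100% would misstate that. The censoring wording matches the row directly above (time to first loss of PASI 90 or relapse). There it fits, because that clock runs within the Maintenance Period, so a carry-over is the likely cause.

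**Working it through.** The SAP gives no event count, rate or precision for this analysis, so there is no figure of its own to reproduce. The check has three steps.

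**1. Censoring time implied by the definitions**

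- Clock start: first dose after relapse is measured (Table AMAK.6.3), given at the relapse visit (SAP Section 5).
- Assessments precede dosing (protocol Schedule of Activities, footnote a), so the relapse PASI falls before the Relapse Period starts.
- Last Maintenance Period visit of a relapser: the relapse visit.
- Censoring time = relapse visit date − Relapse Period start date = 0 days. It is 1 day with the SAP's +1 rule for interval length, and 2 days if the word after also means the day after.
- If the relapse visit is instead assigned by date to the Relapse Period, the last Maintenance visit is one visit earlier and the time is about −28 days, which is impossible.
- First scheduled PASI after the clock starts: the next visit, 4 weeks later.

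With censoring at 0, 1 or 2 days, no non-regainer is at risk at week 4 or later.

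**2. Worked example (hypothetical counts)**

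Ten patients relapse at Week 32. Two regain at 4 weeks, one each at 8, 12 and 16 weeks, and five never regain. Cumulative regain is 1 − ∏(1 − d/r), with d events and r patients at risk.

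| Weeks after retreatment | d | r, literal | Regain, literal | r, censored at Week 52 | Regain, censored at Week 52 |
|---|---|---|---|---|---|
| 4 | 2 | 5 | 40% | 10 | 20% |
| 8 | 1 | 3 | 60% | 8 | 30% |
| 12 | 1 | 2 | 80% | 7 | 40% |
| 16 | 1 | 1 | 100% | 6 | 50% |

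The literal product is 1 − (3/5)(2/3)(1/2)(0/1) = 1.00. With the five censored at 52 − 32 = 20 weeks it is 1 − (8/10)(7/8)(6/7)(5/6) = 0.50. Half the patients regained.

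**3. Illustrative model**

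The documents give no recapture rate, relapse timing or dropout rate. Assumptions: a constant chance p of regaining at each 4-weekly visit, follow-up to Week 52, no dropout at first.

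- p solves 1 − (1 − p)^4 = true 16-week rate. For 0.50, p = 0.159.
- Visits after relapse: n = (52 − relapse week)/4, so n runs from 8 (Week 20) down to 1 (Week 48, the last injection visit).
- Literal curve at visit k = mean[1 − (1 − p)^min(n,k)] / mean[1 − (1 − p)^n].

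True rate 0.50, relapse spread evenly over Weeks 20 to 48:

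| Weeks | 4 | 8 | 12 | 16 |
|---|---|---|---|---|
| True | 0.159 | 0.293 | 0.405 | 0.500 |
| Literal curve | 0.315 | 0.547 | 0.715 | 0.832 |

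At 16 weeks, for example, 0.4197/0.5045 = 0.832.

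Literal 16-week value for other true rates, without dropout and with 5% dropout per visit (simulation of 200,000 relapsers):

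| True 16-week rate | 0.30 | 0.50 | 0.70 | 0.80 |
|---|---|---|---|---|
| Relapse Weeks 20–48, no dropout | 0.783 | 0.832 | 0.889 | 0.921 |
| Relapse Weeks 20–48, 5% dropout | 0.813 | 0.857 | 0.906 | 0.935 |
| Relapse Weeks 20–32, no dropout | 0.686 | 0.747 | 0.823 | 0.870 |
| Relapse Weeks 20–32, 5% dropout | 0.727 | 0.778 | 0.850 | 0.889 |

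Censoring in the Relapse Period returned the true rate to within 0.002 in every case.

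**The case against.** The strongest reply is that Maintenance Period here means all of Weeks 16 to 52. The SAP often uses it so. Section 5 has "Double-Blind Maintenance Period (Week 16 to Week 52): All patients who complete the Induction Period may continue in the Maintenance Period". Table AMAK.4.1 lists "Proportion of patients who regained PASI 90 within 16 weeks after mirikizumab retreatment" under the maintenance dosing period. Table AMAK.6.2 places the Re-randomized Relapsed population under Maintenance, and Table AMAK.6.3 itself describes the dose that admits a patient to the Relapse Period as given during maintenance. The NRI rule in Section 6.3.1 also keeps a relapser's later visits in the maintenance analysis, as non-response. On this reading, censoring falls at the last visit up to Week 52 and the curve is valid. A rule that otherwise yields zero or negative times invites the workable reading.

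That reading is available, and a careful programmer may adopt it. It does not settle the text. The row needs Table AMAK.6.3 for its time zero, and the same table ends Maintenance before Relapse. Section 6.13.1 says relapsers have left the Maintenance Period. For the MMRM in Section 6.3.2, "only the visits prior to entering the Relapse Period will be included in the MMRM model for the Maintenance Period efficacy analysis". An impossible or zero time under the SAP's own definitions shows that the row needs correcting.

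Two further points stand. The percentages apply only if the narrow reading is programmed, so they are not a forecast of bias. The consequence is also small: other planned summaries in the same population would show up a false 100%.

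**Conclusion.** The concern holds, as a minor point. Read with the table that defines its terms, the censoring rule removes every non-regainer before the first possible event. The curve then overstates recapture at every visit and ends at 100% at the last observed regain time, provided at least one patient regains. That structure does not depend on the model. The sizes do: under the stated assumptions, true 16-week rates of 30% to 80% appear as 69% to 94%. Under the broad meaning of Maintenance the bias is nil.

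The reach is one descriptive Kaplan-Meier analysis with no planned comparison, for PASI 90. It extends to PASI 100 only if that is run from the same row, since Table AMAK.6.6 does not schedule it. The as-observed proportion regaining PASI 90 within 16 weeks, the by-visit PASI summaries in relapsed patients and all alpha-controlled endpoints do not use the rule.

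**What to change.** In the censoring cell of this row of Table AMAK.6.5, censor patients who do not regain response after the date of their last PASI assessment during the Relapse Period. That period's end (Week 52 or the early discontinuation visit) is already defined in Table AMAK.6.3, and the rule gives a valid curve whichever way Maintenance is read. A patient with no PASI after retreatment is censored at the clock start and does not affect the curve; a short note could say so.

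The cost is one phrase in the SAP. Data collection, sample size and the alpha-controlled analyses do not change.
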